6.0 MEASUREMENT OF EFFECT

Because this R34 is a planning grant to prepare for an RCT, we will conduct surveys that collect the same information we would collect in an RCT. Questions reflect the information needed to test the primary and secondary outcomes as well as mediation and moderation models. We will measure the time it takes to conduct each survey and assess participant comfort with responding. Table 2 lists items we will ask about in the survey.

Table 2: Measures and scales used in PartnerCHESS study

Measure	Who	Source	Reference	# Questions	Time (month)
Primary outcomes					
Risky drinking days	Patient	TLFB every 60 days (PhenX)	Collins et al. ⁷⁵	1	0, 2, 4, 6
Days of abstinence	Patient	TLFB every 60 days (PhenX)	Collins et al. ⁷⁵	1	0, 2, 4, 6
Secondary outcomes					
Treatment retention	Patient	Clinic records		0	0, 2, 4, 6
Negative affect	Patient & partner	PANAS	Crawford ⁶⁰	10	0, 2, 4, 6
Depression	Patient & partner	PHQ-8		8	0, 2, 4, 6
Sleep quality	Patient & partner	Smartphone data	Sleep Cycle ⁷⁶	0	0, 2, 4, 6
Exploratory outcomes					
Days of other drug use	Patient & partner	TLFB every 60 days (PhenX)	Collins et al. ⁷⁵	2	0, 2, 4, 6
Health service use	Patient & partner	TLFB every 60 days (PhenX)	McCollister, et al. ⁷⁷	8	0, 2, 4, 6
Risky drinking days	Patient & partner	TLFB every 60 days (PhenX)	Collins et al. ⁷⁵	2	0, 2, 4, 6
Physical/psychological abuse	Patient & partner	Rev. Conflict Tactics Scale	Straus et al. ⁷⁸	8	0, 2, 4, 6
Satisfaction with technology	Patient & partner	Technology Acceptance Model ⁷⁹	Szajna ⁸⁰	10	0, 2, 4, 6
Mediators					
Intrinsic motivation	Partner	Brief Self Control Scale.	Tangney ⁸¹	12	0, 2, 4, 6
Intrinsic motivation	Patient	Commitment to sobriety scale	Kelly ⁸²	5	0, 2, 4, 6
Competence	Patient & partner	CCQ and # of skills used.	Schroder ⁸³	9	0, 2, 4, 6
Relatedness	Patient & partner	Bonding	Kim ⁸⁴	5	0, 2, 4, 6
Moderators					
Gender/Sex	Patient & partner	Question (PhenX tier 1)	Collins et al. ⁷⁵	1	0
PartnerCHESS use	Patient & partner	Smartphone data	McTavish ⁸⁵	0	0, 2, 4, 6
A-CHESS use	Patient	Smartphone data	McTavish ⁸⁵	0	0, 2, 4, 6
Covariates					
Age	Patient & partner			1	0
Education	Patient & partner			1	0

Race/ethnicity	Patient & partner			2	0
Relationship status	Patient & partner			1	0, 2, 4, 6
Psychiatric treatment history	Patient & partner	Question (PhenX tier 1)	Collins et al. ⁷⁵	1	0
Baseline of outcomes	Patient & partner	See rows above	Collins et al. ⁷⁵	11	0

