Data analysis plan. The analysis will: (1) determine if there is a significant difference between study arms over the 6-month pilot test, and (2) explore the conceptual model (Figure 1)—i.e., the relationships between the primary and secondary outcomes and patient and partner mediators, moderators, the 2 study arms, and covariates. We will report descriptive statistics for all demographic and clinical variables in both arms to ensure that randomization produced demographically and clinically comparable groups; if not, variables with significant differences will be included as covariates in a sensitivity analysis. Analysis of the impact of PartnerCHESS+TAU vs. A-CHESS+TAU will focus on outcomes over time computed from data at pretest, 2, 4, and 6 months, with separate models for the primary outcomes and each secondary outcome. Linear mixed effects models—which account for dependence among successive observations on the same patient and incomplete data—will analyze outcomes longitudinally and at each time point. Initial intercepts will be modeled as random variables to provide variance and covariance estimates of intervention effects at each time point and across and between patients. A generalized linear mixed effects model, based on a multiple regression, will be used for the continuous outcome of risky drinking days.⁸⁹ We will conduct specific treatment time contrasts both between and within groups to test time-based effects. Sensitivity analyses (with and without covariate adjustment) will determine the robustness of covariate-related error control.

Modeling mediation and moderation. For both patients and partners, we will test the effect of the interventions on potential mediators (competence, intrinsic motivation, and relatedness) on primary and secondary outcomes, using Barron and Kenny's⁹⁰ steps: Step 1, the outcomes (e.g., risky drinking days) will be regressed on the interventions (arm 1 vs. arm 2); Step 2, mediators will be regressed on the interventions; Step 3, the intervention variable and mediator variables will be regressed on the outcomes.

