Mediator effects are statistically significant if: (a) the beta-weight coefficients in Steps 1 and 2 differ significantly from zero, (b) the Step 3 beta-weight coefficient of the mediators is statistically significant, and, (c) the difference between the beta-weight coefficients of the intervention variable in Steps 1 and 3 is statistically greater than zero. We will test whether patient and partner gender moderates the effect of intervention on outcomes. We will derive interaction terms for the predictor variables, incorporating them into the regression model, and determine whether those terms significantly contribute to the outcome predictions that exist independent of other significant contributors. We will examine moderated mediation because the process may be more complex than can be rendered by treating the factors independently (e.g., a mediator may be stronger for women than men or vice versa). We will develop a moderated mediation structure to determine whether the results are best described by meaningful higher-order interaction terms based on mediator-moderator combinations.

Power. We understand that estimating effect size from pilots can lead to bad estimates. A paper by Leon, Davis, and Kraemer² points out that a pilot study can evaluate the. It informs feasibility and identifies modifications needed before a larger hypothesis-testing study. But (they argue) a pilot study does not provide meaningful effect size estimates for planning subsequent studies because of the imprecision inherent small samples. Rather, a hypothesis-testing study should be designed to detect the smallest difference that is generally agreed to be clinically meaningful. Several studies (e.g. Walters et al.)³ suggest that an effect size of $d=.35$

is considered clinically meaningful. So we will use $d=.35$ at a power of .85 to determine sample size needed for the large study.

This particular pilot is not powered to detect any effect on outcomes. Once the R34 analyses are complete, we will develop the R01 proposal based on the previous work mentioned above but also considering what we learn about the feasibility of recruitment, randomization, retention, assessment procedures, and new methods mentioned above.

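### Goal (1) and the mediation rule call for significance decisions that the plan itself says the pilot is not powered to support

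*Combined protocol and SAP*

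**What the plan says.** The Data analysis plan in section 8.0 has two goals. The first is to "determine if there is a significant difference between study arms over the 6-month pilot test"; only the second, on the conceptual model, is worded as exploration. The models "will analyze outcomes longitudinally and at each time point", "with separate models for the primary outcomes and each secondary outcome". The plan adds "specific treatment time contrasts both between and within groups to test time-based effects". Table 2 in section 6.0 lists two primary outcomes, risky drinking days and "Days of abstinence". Section 8.0 gives no alpha, no sidedness and no multiplicity rule.

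Under Modeling mediation and moderation, condition (a) for a significant mediator is that "the beta-weight coefficients in Steps 1 and 2 differ significantly from zero". Step 1 is the regression of outcome on arm. Condition (b) requires a significant mediator coefficient in Step 3. Condition (c) requires the fall in the arm coefficient from Step 1 to Step 3 to be significantly above zero.

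The Power paragraph says: "This particular pilot is not powered to detect any effect on outcomes". It argues that pilots give effect sizes too imprecise for planning, and takes d = .35 "at a power of .85 to determine sample size needed for the large study". It names recruitment, randomization, retention and assessment procedures as lessons for the R01 proposal. The project summary, by contrast, gives effect-size estimation as a purpose of the pilot and says the survey data will show whether a large trial is promising. Section 2.0 states the same aim as feasibility.

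**The concern.** Goal (1) and condition (a) each require a yes/no answer from a significance test, and the Power paragraph says the pilot is not built to give one. A non-significant result would say little, because an effect of the size the plan calls clinically meaningful would usually be missed. A significant result would tend to overstate the effect, because only estimates above d = .35 can reach significance. It could also arise from one of several unadjusted tests. Requiring a significant Step 1 effect adds a low-powered test to a mediation rule that is already weak. At stake is how the pilot's results are read, and whether a p-value informally colors the judgment on the R01.

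**Working it through.** **Inputs from the documents.** 34 dyads randomized 1:1 (section 7.0); about 10% dropout, leaving about 15 dyads per arm (section 5.0); surveys at baseline, 2, 4 and 6 months; d = .35, set for the later trial (section 8.0, Power).

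**Assumptions.** Two-sided 5%, normal outcomes with SD 1, equal correlation r between visits of .3–.7. The planned model for risky drinking days may behave differently.

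**The plan's own figure.** 34/2 = 17 per arm; 17 × 0.90 = 15.3. This reproduces about 15, so I use n = 15 and n = 17.

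**Power and significance threshold.** Power comes from the noncentral t with noncentrality .35 × √(n/(2v)), where v is the variance factor. The smallest significant estimate, which equals the 95% half-width, is t(.975, df) × √(2v/n).

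- Unadjusted single visit: v = 1, df = 2n − 2.
- Unadjusted mean of three follow-ups: v = (1 + 2r)/3, df = 2n − 2.
- Baseline-adjusted mean: v = (1 + 2r)/3 − r², df = 2n − 3.

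| Test | v | Power, n = 15 / 17 | Threshold d, n = 15 / 17 |
|---|---|---|---|
| Single visit, unadjusted | 1 | 15.3% / 16.8% | 0.75 / 0.70 |
| Mean of three, unadjusted, r = .3 | .533 | 24.5% / 27.3% | 0.55 / 0.51 |
| Mean of three, unadjusted, r = .7 | .800 | 17.9% / 19.8% | 0.67 / 0.62 |
| Mean of three, adjusted, r = .3 | .443 | 28.4% / 31.8% | 0.50 / 0.47 |
| Mean of three, adjusted, r = .7 | .310 | 38.2% / 42.7% | 0.42 / 0.39 |

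The adjusted test passes 50% power only at r of about .80 (n = 15) or .77 (n = 17). For scale, d = .35 at power .85 needs 2 × (1.960 + 1.036)²/.35² ≈ 147 per arm.

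**Multiplicity under no effect.** Simulated with baseline-adjusted tests, visit correlation .5 and correlation between the two outcomes of .3–.9.

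- Two overall tests only: at least one p < .05 in about 7–9% of trials (ceiling for independent tests: 1 − .95² = 9.75%).
- Two outcomes × (overall + three visits) = eight tests: about 20–26%.

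**Mediation.** Assumed full mediation, with arm-to-mediator effect a, mediator-to-outcome effect b, total effect a × b = .35, and within-arm SDs of 1. Condition (c) is not yet applied.

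| a, b | n | Steps 2–3 significant | Steps 1–3 significant |
|---|---|---|---|
| .5, .7 | 15 | 26% | 10.5% |
| .7, .5 | 15 | 36% | 8.9% |
| .5, .7 | 17 | 29% | 12.1% |
| .7, .5 | 17 | 43% | 11.1% |

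Simulation runs differ by up to about a point. Steps 2–3 therefore pass in roughly 26–44% of trials, and adding Step 1 cuts this to about 9–12%.

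**The case against.** The strongest reply is that little depends on the wording. The Power paragraph concedes the lack of power, sizes the large trial on d = .35 and names feasibility inputs. Section 2.0 states the aim as feasibility. This stands, and it limits the consequence. It does not remove the conflict, because goal (1) and condition (a) remain in force as written.

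Goal (1) concerns the whole six months, and the plan says the analysis focuses on outcomes over time. The longitudinal comparison is therefore the natural test. This also stands. A reader might infer that a significant estimate must be at least twice d = .35; that holds only for an unadjusted single visit (0.70–0.75). For the adjusted six-month mean the threshold is 0.39–0.50, or 1.1–1.4 times. A reader might likewise take about 25% as the false-positive rate. That needs all eight tests to count; the two-test reading gives 7–9%. The plan permits both readings, because it also analyzes each time point and states no multiplicity rule.

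On mediation, condition (c) already tests the indirect effect: in a linear model the Step 1 minus Step 3 difference is that effect. The plan does not overlook it. Mediation also sits under the exploratory goal, and condition (a) governs what is called significant, not which models are fitted. What remains is that a significant Step 1 effect is still required.

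**Conclusion.** The concern holds in limited form. Section 8.0 sets a significance decision between arms as its first goal and makes a significant arm effect a condition for mediation, while disclaiming power for any outcome effect. That contradiction is in the text and needs no assumption. Its size depends on the assumptions listed: power of 28–43% for the adjusted six-month mean at d = .35 (18–27% unadjusted), 15–17% for an unadjusted single visit, and a fall from about 26–44% to 9–12% when Step 1 is added to the mediation rule.

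Two stronger readings are not supported. A reader might infer that the R01 decision turns on statistical significance. No such rule is stated; the project summary only leaves open which results would count as promising. A reader might also infer that low power inflates the error rate of a single test. It does not: a significant result is unreliable here because of exaggeration and uncontrolled multiplicity. This should be fixed, but it does not undermine the pilot's feasibility purpose.

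**What to change.** 1. Reword goal (1) and the time contrasts as estimation of between-arm differences with 95% confidence intervals, labelled exploratory, with no efficacy claim drawn from p-values. State the expected half-widths: about 0.39–0.50 SD for the baseline-adjusted six-month mean, 0.51–0.67 SD unadjusted, and 0.70–0.75 SD for an unadjusted single visit.
2. Remove the Step 1 significance requirement from condition (a). Report the indirect effect that condition (c) already targets with a bootstrap 95% interval, labelled exploratory. It should not become a new pass/fail rule: in the scenarios above it excludes zero in only 30–46% of trials and is about 0.8–1.0 SD wide around a true .35.
3. Reconcile the project summary with section 2.0 and the Power paragraph. Rest the R01 decision on the feasibility results named there, and keep sizing on d = .35.

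No new data or participants are needed. The cost is that the team gives up significance verdicts on arms and mediators and replaces the named stepwise rule. The change should be settled before outcomes are analyzed by arm.

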We believe that recruitment will accrue faster than normal for couples therapy because costs for internet coverage will be paid and partners will not have to visit the clinic at all (even phone delivery can be provided at a more convenient location). Hence the incentive is high and the stigma in participating is low. If either the patient or the partner declines, the dyad will be excluded. To help us prepare for an R01, we will measure the number and percent of patients who are eligible and accept, the number and percent of partners who accept, and the number of dyads that join. We will document reasons for any refusal and monitor whether refusal rates differ by patient and partner sex, race, and age. Based on the results, the recruitment process for the R01 may need to change. We will note whether partners are of the opposite or same sex. To avoid coercion, SSTAR will be paid on a fixed-price contract rather than a per-couple-recruited basis.

Patient Randomization: The 6 dyads recruited to take part in the initial development phase will not be randomized. For the 34 dyads taking part in the pilot study, we will use www.randomization.com to stratify on patient gender so the A-CHESS and PartnerCHESS groups have the same proportions of men and women patients, balancing on same-sex couples, age, and race. When the baseline survey is complete, the UW Study Coordinator will enter participant numbers and randomization data through a secure internet line to the www.randomization.com website.

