7.0 STUDY PARAMETERS

40 dyads will be recruited, 6 of whom will participate in development and initial testing of PartnerCHESS and the survey instruments. The remaining 34 dyads will be randomized on a 1:1 ratio to either A-CHESS + TAU or PartnerCHESS + TAU. Subjects will be stratified by gender and have access to A-CHESS or PartnerCHESS for 6 months.

Patients will have access to A-CHESS and Patients/Partners will have access to Partner CHESS for the 6 months of the study. They will be allowed to keep the phone, so that they could continue to use those interventions if they had other ways to access the two systems. Partners in the A-CHESS group will not have access to either app.

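### The arm-comparison models omit the stratification factor (patient gender) and leave the use of the pretest value open: a minor point, at no cost to fix beyond SAP wording

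*Combined protocol and SAP*

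**What the plan says.** Section 4.0 (Patient Randomization) will "stratify on patient gender so the A-CHESS and PartnerCHESS groups have the same proportions" of men and women patients, while "balancing on same-sex couples, age, and race". Section 7.0 repeats the first part: "Subjects will be stratified by gender".

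Section 8.0 (Data analysis plan) gives as its first analytic aim to "determine if there is a significant difference between study arms over the 6-month pilot test". The comparison concerns "outcomes over time computed from data at pretest, 2, 4, and 6 months", with a separate model for the primary outcomes and for each secondary outcome. Linear mixed models with random intercepts "will analyze outcomes longitudinally and at each time point"; a generalized mixed model is used for risky drinking days. No fixed-effect covariate is named for any of these models.

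Two sentences mention adjustment of the arm comparison, and both concern sensitivity analyses. One applies when the arms turn out not to be comparable at baseline: "if not, variables with significant differences will be included as covariates in a sensitivity analysis". The other reads: "Sensitivity analyses (with and without covariate adjustment) will determine the robustness of covariate-related error control". It gives no covariate list.

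Table 2 (section 6.0) has a covariates block that includes the baseline values of the outcomes, and it lists gender as a moderator. Section 8.0 then uses gender in interaction tests, and covariates in exploring the conceptual model. Neither use defines the main arm comparison.

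**The concern.** A factor used to stratify the randomisation belongs in the main model. If gender is prognostic and is left out, the model-based standard error still contains the between-gender variation that the design has balanced away. The test is then conservative.

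Pretest is both one of the four analysed time points and, in Table 2, a covariate. Section 8.0 does not say whether its mean is free or common across arms, or how it enters the comparisons at individual time points. Three estimates therefore fit the text: follow-up only, change from pretest, and baseline-adjusted. They have different standard errors, and which of the first two is the less precise depends on a correlation unknown until the data are in.

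Choosing covariates by significant baseline differences is a weak rule at this size. It responds to chance imbalance rather than to prognostic value, and it misses imbalances of moderate size.

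At stake are the planned significance test, the effect-size estimate named in the aims, and the goal in section 2.0 of settling the analytical protocol for the larger trial.

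**Working it through.** **Inputs from the documents.** 34 dyads randomised 1:1, so 17 per arm (section 7.0); dropout of about 10%, leaving about 15 per arm (section 5.0). Check: 17 × 0.90 = 15.3, which agrees.

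**Assumptions (the documents give no values).** Linear model; outcome SD of 1; two-sided 0.05; equal correlation ρ of .3, .5 or .7 between any two visits, as a random intercept implies.

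**1. Mean of months 2, 4 and 6, with 15 per arm.** The variance of the arm difference is 2/15 times:
- follow-up only: (1 + 2ρ)/3 = 0.533 / 0.667 / 0.800
- change from pretest: 4(1 − ρ)/3 = 0.933 / 0.667 / 0.400
- baseline-adjusted: (1 + 2ρ)/3 − ρ² = 0.443 / 0.417 / 0.310

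If the baseline slope is estimated as a covariate, the last line is multiplied by 1 + 1/26. Taking square roots:

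| Estimate | SE, ρ = .3 | SE, ρ = .5 | SE, ρ = .7 |
|---|---|---|---|
| Follow-up only | 0.267 | 0.298 | 0.327 |
| Change | 0.353 | 0.298 | 0.231 |
| Adjusted, baseline as covariate | 0.248 | 0.240 | 0.207 |
| Adjusted, common pretest mean (large-sample) | 0.243 | 0.236 | 0.203 |

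With baseline as covariate, the variance is about 51/35/20% below change and 14/35/60% below follow-up only. The two adjusted forms are practically equal.

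**2. Single follow-up visit, with 15 per arm.** Follow-up only: √(2/15) = 0.365. Change: √(2/15 × 2(1 − ρ)) = 0.432 / 0.365 / 0.283. Adjusted: √(2/15 × (1 − ρ²) × (1 + 1/26)) = 0.355 / 0.322 / 0.266. At ρ = .3 the gain in SE over follow-up only is just 3%.

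**3. Leaving out gender.** Assume 9 men and 6 women per arm, within-gender SD 1 and a gender difference of δ. The expected residual variance of the unadjusted model is 1 + 2 × (9 × 6/15) × δ²/28 = 1 + 0.257δ², whereas the arm difference varies as if it were 1. At δ = 1, √1.257 = 1.121, so the critical value of 2.048 acts like 2.048 × 1.121 = 2.30 on 28 df, a true size of about .029. Simulation under the null (2,000,000 trials per setting) gave .048, .044, .035 and .029 for δ = 0.3, 0.5, 0.8 and 1.0. With gender in the model, the size was .049 to .051.

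**4. The baseline-significance rule, with 17 per arm.** The smallest difference flagged is t(.975, 32) × √(2/17) = 2.037 × 0.343 = 0.70 SD. By the normal approximation, a chance imbalance above 0.5 SD arises in about 14% of trials, and about 10% fall between 0.5 and 0.70 SD, unflagged. In the other direction, 10 independent baseline tests give 1 − 0.95^10 = 40% chance of at least one false flag.

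**The case against.** The strongest objection is that the pilot's arm contrast decides little. Section 8.0 (Power) says the pilot is not powered to detect any effect on outcomes, questions the use of pilot effect sizes for planning, and sizes the larger study from d = .35. That stands, and it is why the point is minor. It does not remove the matter, because the same section still plans a test between arms and the aims still speak of estimating effect size.

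Second, baseline adjustment may already be intended. The Table 2 covariates block is the natural reading of the with-and-without-adjustment sentence, and the risky-drinking model is described as based on a multiple regression. This is plausible, but it yields at most an unlisted sensitivity analysis and does not fix the main model.

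Third, the sizes are weakest where they matter most. Risky drinking days uses a generalized model, the larger percentages come from the ends of an assumed correlation range, and a gender difference of 0.3 SD barely moves the test. The sex-specific cutoffs for risky drinking may keep the gender difference small. All of this is fair.

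Four stronger readings might be inferred, and the documents do not support them:
- *That the planned comparison is biased.* It is not; over randomisation the unadjusted comparison is unbiased.
- *That type I error is inflated.* Omitting a balanced prognostic factor lowers the error rate.
- *That the significance rule distorts the main result.* It governs only a sensitivity analysis.
- *That gender and baseline are missing from the plan.* Both are in it, with roles outside the main arm comparison.

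**Conclusion.** The point holds as a minor improvement. Section 8.0 leaves the stratification factor out of the models that compare the arms, does not fix the use of pretest, and leaves adjustment to sensitivity analyses, one of which has a poor selection rule. The consequences are lost precision, a conservative test if gender is prognostic, and an analysis choice left open. Baseline adjustment has the smallest standard error in every case examined; for the three-visit mean, the variance saving is about 14 to 60% depending on the comparator and the correlation.

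These sizes rest on a linear model, equal correlations of .3 to .7, 15 completers per arm and, for gender, assumed differences and strata. They need not carry over to the generalized model of risky drinking days.

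**What to change.** In section 8.0 (Data analysis plan):

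- Enter patient gender as a fixed effect in every main arm-comparison model.
- For primary and secondary outcomes measured before randomisation (risky drinking days, days of abstinence, negative affect and, as listed in Table 2, depression), keep pretest, 2, 4 and 6 months as responses and constrain the pretest mean to be equal across arms. This keeps patients with no follow-up survey and the planned within-group contrasts. In the generalized model of risky drinking days, the baseline value as a covariate is an acceptable alternative, although patients with no follow-up then drop out of that model.
- Take the by-time-point and 6-month contrasts from this one model.
- For secondary outcomes without a pre-randomisation value, adjust for gender only. These are treatment retention, and smartphone sleep quality where no reading precedes randomisation. Some participants use their own phones, so this should be settled explicitly for sleep.
- Replace selection by baseline significance with a prespecified set (age, race, same-sex-couple status) in the adjusted sensitivity analysis. About 30 completers cannot carry all of these in the main model. Report baseline tables descriptively.
- Report the unadjusted model as a sensitivity analysis.

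The cost is SAP wording and one or two degrees of freedom. Gender and the baseline survey are already collected before randomisation (sections 4.0 and 6.0).

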Missing data. In previous RCTs, we completed about 85% of surveys through 12 months and kept missing data on core survey items to about 2%. We expect these rates in this study. In addiction treatment, data are not likely to be missing at random (i.e., the probability that data are missing relates to what the data would have been had they been observed). For example, a patient may not want to disclose some information in surveys. Because this may lead to biased parameter estimates, we will identify missing data patterns and use pattern-mixture modeling to test the sensitivity of our analysis to missing data assumptions⁹¹⁻⁹⁴ and conduct other sensitivity analyses after imputing missing data with a range of plausible values based on assumptions for the missing data (e.g., best-case, worst-case; with and without multiple imputation).⁹⁵⁻⁹⁷

Intention-to-treat and subject noncompliance. Standard intention-to-treat (ITT) estimates the average treatment effect by comparing outcomes based on assignment of the treatment, but ignoring use of the treatment. Because ITT effect estimates do not represent treatment efficacy under noncompliance (e.g., a patient is randomized to PartnerCHESS but does not use the system), we will estimate noncompliance by also estimating treatment effects only for compliers using As-treated, Per-Protocol⁹⁸ and CACE.⁹⁹

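### Section 8.0 names only a random intercept for the linear mixed models; if fitted that way and visit correlation decays, long-lag change contrasts run at about 6-11% type I error, so the covariance and degrees-of-freedom method should be stated

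*Combined protocol and SAP*

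**What the plan says.** All of this is in Section 8.0, mainly under the data analysis plan. Outcomes come from pretest and months 2, 4 and 6, and linear mixed models "will analyze outcomes longitudinally and at each time point". On the random part of these models, the plan states that "intercepts will be modeled as random variables to provide variance and covariance estimates of intervention effects at each time point and across and between patients". The models are also said to allow for dependence among a patient's repeated observations. The stated purpose includes to "determine if there is a significant difference between study arms over the 6-month pilot test", and "We will conduct specific treatment time contrasts both between and within groups to test time-based effects".

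One primary outcome is treated differently: "A generalized linear mixed effects model, based on a multiple regression, will be used for the continuous outcome of risky drinking days". The paragraph on power adds that "This particular pilot is not powered to detect any effect on outcomes".

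No random slope, residual covariance structure, degrees-of-freedom method, significance level or visit correlation is given anywhere in the document. The planned sensitivity analyses cover covariates, missing data and noncompliance. None varies the covariance structure.

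**The concern.** A random intercept with independent, equal-variance residuals forces one common correlation on all six pairs of the four visits. Repeated measures taken over six months often correlate less as the gap widens. When that happens, the model overstates the correlation between pretest and month 6. The standard error of a change over that gap is then too small, and the standard error of a change between adjacent visits is too large.

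Two things are at stake: false-positive change contrasts, and intervals that look more precise than they are. Section 2.0 makes settling the analytical protocol one purpose of the pilot, so the choice may carry into the later full trial. Two analysts following the present text could also fit different models and get different p-values for the same contrast.

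**Working it through.** **Inputs from the documents**
- "The remaining 34 dyads will be randomized on a 1:1 ratio" (Section 7.0), so 17 per arm.
- Section 5.0 expects about 10% dropout and about 15 dyads per arm completing. Check: 17 × 0.90 = 15.3, which agrees.
- "In previous RCTs, we completed about 85% of surveys through 12 months", and the plan expects the same here.
- Four visits: pretest and months 2, 4 and 6.

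**Assumptions.** Two-sided 5% level; Gaussian outcomes; equal variances unless noted; the correlations shown below.

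**Closed form, complete data.** For arm by (month 6 minus pretest), the true variance divided by the variance the intercept-only model assumes is

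V = (1 − ρ between pretest and month 6) / (1 − mean of the six pairwise ρ).

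Type I error is 2 × [1 − Φ(c/√V)]. The table uses c = 1.96, and c = 1.985, the t critical value on 96 df (34 × 3 − 2 × 3 = 96).

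Example, AR(1) .5: mean ρ = (3 × .5 + 2 × .25 + .125)/6 = .354; V = .875/.646 = 1.355; 1.96/√1.355 = 1.68, which gives 9.2%.

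| Correlation at 2, 4, 6 months apart | V | Error, c = 1.96 | Error, c = 1.985 |
|---|---|---|---|
| Constant | 1.000 | 5.0% | 4.7% |
| AR(1) .3 | 1.193 | 7.3% | 6.9% |
| .70, .65, .60 | 1.200 | 7.4% | 7.0% |
| .60, .50, .40 | 1.286 | 8.4% | 8.0% |
| AR(1) .5 | 1.355 | 9.2% | 8.8% |
| AR(1) .7 | 1.530 | 11.3% | 10.9% |

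Weaker decay gives 5.6% at AR(1) .1 and 6.4% at .2 (c = 1.96). A stable person component s does not help: each 1 − ρ is multiplied by (1 − s), which cancels in V.

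**Other contrasts (c = 1.96)**
- Mean of months 2-6 minus pretest: 6.3-8.3% at AR(1) .3-.7.
- Adjacent visits: 3.4% down to 1.9% at AR(1) .3-.7, so conservative. At .7, V = .30/.4295 = 0.70.
- All-visit average arm difference, and month-6 arm difference with equal variances: 5.0%.

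**Simulation, 17 per arm.** There were 4,000 null trials per setting (Monte Carlo error about 0.35 points), using REML with Kenward-Roger for both models. The data were complete, or had 10% dropout, or had dropout plus sporadic misses leaving about 85% of surveys. Ranges are across these three patterns.

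| Correlation | Random intercept | Unstructured / random-intercept interval width |
|---|---|---|
| Constant .5 | 4.5-5.2% | 1.02-1.03 |
| AR(1) .3 | 6.7-7.2% | 1.11-1.12 |
| .70, .65, .60 | 6.6-7.3% | 1.12 |
| .60, .50, .40 | 7.2-8.3% | 1.15-1.16 |
| AR(1) .5 | 7.9-9.0% | 1.18-1.19 |
| AR(1) .7 | 9.9-11.1% | 1.24-1.27 |

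Unstructured with Kenward-Roger stayed at 4.4-5.4% throughout these simulations. AR(1) .9, beyond the range I would headline, gave 12.0-13.4% for the random intercept.

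**Further simulations, each follow-up visit missing with probability .15**
- 15 per arm, AR(1) .6: random intercept 10.7%, unstructured 6.1%.
- 15 per arm, constant .5: 5.2% and 5.7%.
- 17 per arm, AR(1) .6, SD rising from 1 to 1.3: the month-6 arm difference is itself inflated with the random intercept (8.5%) and not with the unstructured model (5.1%).
- The unstructured model converged in all 44,000 trials of this set (11 settings × 4,000).

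**The case against.** The strongest reply is that the plan never commits to an intercept-only model. It says dependence is allowed for, and it promises variance and covariance estimates at each time point, which sits badly with a single common variance. That stands: this is silence in a short plan, and the error rates hold only if the model is fitted as named. Silence still leaves the choice open after the data are seen.

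Second, month 6 minus pretest is not named as a contrast. The stated aim of comparing arms over six months, and the analysis at each time point, are more naturally read as the all-visit average and the visit-specific differences. A reader might infer that the main arm comparison is inflated. The documents do not support that: the average is unaffected, and so is the month-6 difference when variances are equal. The exposure lies in the treatment-by-time contrasts, which are planned but not listed.

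Third, the pilot is declared unpowered for outcomes, and the later trial is to be sized on d = .35, so an inflated pilot contrast would not set its sample size. That limits the consequence. It does not remove it, because significance tests are still planned.

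Fourth, the simulations are Gaussian with visits missing at random, whereas the plan expects missingness related to the unseen values. That is a fair limit. Days of abstinence in a 60-day window is bounded, so the figures may transfer less well to it.

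**Conclusion.** The point holds as a cheap improvement. If the model has only a random intercept with independent equal-variance residuals, and visit correlation decays, long-lag change contrasts are tested at about 6-11% in place of 5%. There is no inflation under constant correlation, and adjacent-visit contrasts err the other way. The size rests on assumed correlations and an assumed two-sided 5% level.

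The scope is outcomes modelled as Gaussian: negative affect, depression and sleep quality in Table 2, and days of abstinence if fitted linearly. Risky drinking days has its own generalized model and is outside it.

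A reader might also infer that the remedy costs only 2-3% in interval width whatever the truth. That figure applies only when correlation is constant, where it is mainly the change from 96 to 32 degrees of freedom. Under the decay that produces the 7-11% error rates, intervals widen by about 11-27%. That is restored coverage and not lost efficiency.

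**What to change.** Add one or two sentences to Section 8.0 for outcomes analysed with linear mixed models:
- Fixed effects are arm, categorical visit and arm-by-visit.
- The covariance over pretest and months 2, 4 and 6 is unstructured.
- Estimation is by REML, with Kenward-Roger standard errors and degrees of freedom.
- Patient and partner outcomes are fitted in separate models.
- If the model does not converge, keep the random-intercept model with CR2 cluster-robust standard errors, clustered on the person analysed, and Satterthwaite degrees of freedom.

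**Cost.** These are standard software options. If correlation is constant, intervals are about 2-3% wider with the unstructured model and 1.6-2.7% wider with the fallback. At 15 per arm with missing visits, control is approximate (6.1% in one setting). Across the contrasts simulated, the fallback ran at 4.1-5.8%, but it keeps the random-intercept point estimates and was not examined under outcome-dependent dropout. Skewed real data may converge less readily than simulated data, so the fallback should be named in advance.
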